The greatest potential eventual implication of the proposed research is to improve the standard of care for a sizeable population in need of improved treatment approaches: young adults with SUD and emotional distress. If the adjunctive UP proves incrementally effective when added to TAU, it will contribute to evidence-based treatment guidelines for this underserved population. Effectively treating this group would reduce long-term disability and costs, improving overall functioning and reducing public health burden. By delivering adaptive strategies for emotional responding, this transdiagnostic group intervention offers a low cost, easily implemented treatment that may provide greater and more broad-based benefits than existing pharmacological and single-diagnosis therapies, and perhaps help prevent future SUD relapse. Eventual findings may be used to inform the development of guidelines for treatment of young adults (and potentially, other cohorts) with SUD and co-occurring emotional distress. This pilot study is the first, necessary step in obtaining preliminary data for future grant applications (e.g., K awards) to conduct a larger randomized trial adequately powered to examine short- and long-term efficacy, as well as intervention moderators (e.g., SUD type) and mediators.

II. SPECIFIC AIMS

We propose to conduct a pilot randomized controlled trial comparing a cognitive-behavioral, transdiagnostic, emotion-focused group intervention plus treatment as usual (UP + TAU) to TAU alone to within an existing comprehensive outpatient program for young adults with SUD and comorbid emotional distress (N=50). Participants will be randomized in a 2:1 ratio to UP + TAU or TAU alone conditions

Specific Aim 1: To evaluate the acceptability and feasibility of adding a transdiagnostic, emotion-focused group intervention (16 twice-weekly UP sessions) to TAU in a comprehensive outpatient program for young adults with SUDs and elevated emotional distress (N=50).

Hypothesis 1a. UP participants will report high satisfaction with and acceptability of the UP per Client Satisfaction Questionnaire (CSQ-8⁴⁷) and semi-structured clinical feedback interview.

Hypothesis 1b. UP participants will be less likely to drop out from treatment at the outpatient program during the study period than those in control condition.

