Specific Aim 2: To explore the adjunctive intervention's acute efficacy in treating emotional distress (anxiety, depression, suicidal ideation, NSSI) and indices of SUD (commitment to sobriety, craving, quantity and frequency of substance use).

Hypothesis 2a. UP participants will evidence greater decreases in Overall Anxiety Severity and Impairment Scale (OASIS) and Overall Depression Severity and Impairment Scale (ODSIS) from pre- to post-treatment than the those in the control condition. Hypothesis 2b. UP participants who report past month suicidal thoughts at baseline will evidence greater reductions in Beck Scale for Suicidal Ideation (BSI⁴⁹) scores from pre-to post-treatment than those in the control condition.

Hypothesis 2c. UP participants who report past month NSSI urges or episodes at baseline will report a lower frequency of NSSI urges and episodes in a one-month period on the Self-Injurious Thoughts and Behaviors Interview-Clinician Rated [SITBI-CR⁵⁰]-

and on the Self-Injurious Thoughts and Behaviors Interview-Self-Rated [SITBI-SR⁵⁰] at post-treatment than the control.

Hypothesis 2d. UP participants will evidence greater increases in Commitment to Sobriety Scale (CSS⁵¹) and decreases in Craving Scale⁵² scores from pre- to post-treatment than the control.

Hypothesis 2e. UP participants will report lower quantity and frequency of substance use during the study period than those in the control condition.

III. SUBJECT SELECTION

We propose to conduct a pilot randomized controlled trial for young adults with SUD and comorbid emotional distress who are entering into or currently engaged in treatment within a comprehensive outpatient program (ARMS at MGH). We plan to enroll 50 young adults (ages 18 to 26) with SUD and comorbid emotional distress from ARMS. They will be randomized in a 2:1 ratio to one of two conditions: 16 twice-weekly sessions of a transdiagnostic, group-based CBT intervention (the Unified Protocol [UP]) plus usual services at ARMS (UP + TAU condition) or treatment as usual at ARMS (TAU; control condition). All potential subjects must satisfy the following inclusion/exclusion criteria upon the study screening visit:

Inclusion criteria:

- 1. Young adults ages 18 to 26, inclusive
- 2. English language proficiency
- 3. Ability to provide written, informed consent
- 4. Ability to attend in-person, outpatient sessions

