measures of anxiety or depression used for clinical purposes at ARMS, and/or report of suicidal thoughts or NSSI in the past week) will be enrolled in the study. An ARMS clinician will determine possible subject eligibility based on information obtained during the routine clinical evaluation for ARMS treatment. Those who are deemed potentially eligible and express interest in the study will then undergo a brief in-person screening visit with a study clinician. The screening visit, which will take about 60 minutes, will consist of a meeting with a study clinician to provide informed consent and confirm study eligibility (via review of information obtained during routine ARMS clinical care and completion of the SITBI-CR). For participants who report suicidal thoughts in the past week or having made a suicide plan or suicide attempt in the past year on the SITBI-CR, a clinical risk assessment (including severity of ideation and presence of plan, intent, and access to means) will be conducted during the visit in order to ensure participant safety and eligibility for the study (i.e., no imminent suicide risk). The study clinician conducting the screening visit will consult the ARMS Clinical Director (or, if [name] is unavailable, another licensed clinician on-site) immediately regarding risk in any questionable cases to determine the appropriate action, per usual ARMS clinical procedures. Eligible participants will then complete the Timeline Follow Back (TLFB^{53,54}) as an interview, in which participants recall the quantity and frequency of substance use during a specified time window (e.g., past month) using a calendar, and several self-report questionnaires, including the BSI, CCS, and Craving Scale (see Table 1). The study clinician will also fill out a concomitant treatment log to identify the participant's overall treatment plan, including medication and therapy. Data obtained at this screening visit will be considered the "pre-treatment" assessment. After eligibility criteria are determined and participants have completed the screening/baseline assessment, participants will be randomly assigned to UP+TAU or TAU only conditions using a permuted block randomization procedure. The permuted block randomization schedules will be generated by an independent biostatistician from the MGH Biostatistics Center prior to enrolling the first subject into the study. Groups, or "blocks," of 5 individuals will be randomized at a time to one of the two treatment conditions (UP+TAU or TAU alone) using a 2:1 randomization scheme, defined as 2 blocks randomized to UP + TAU for every 1 block randomized to TAU alone. Randomizations will be conducted using a web-based randomization program developed by the MGH Biostatistics Center. The randomization code will be generated within the webbased program by study staff only when the randomization occurs, i.e. once the last participant of each group has completed baseline. Participants will then be contacted by study staff via their preferred method of communication to notify them of their study condition.

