Specific Aim 2: Analyses will be intention-to-treat, such that participants will be analyzed as part of their allocated group irrespective how much treatment was received. Continuous variables (OASIS, ODSIS, BSI, CSS, and Craving Scale scores, frequency of NSSI urges and episodes captured by the SITBI, quantity and frequency of substance use, percent days abstinence [PDA]) will be analyzed with generalized mixed effect modeling, which imputes missing values based on maximum likelihood estimates of missing parameters (*Hypotheses 2a, 2b, 2c, 2d, 2e*). Time-by-condition interactions will be analyzed to test the efficacy of the adjunctive intervention. Known confounding variables (e.g., age, gender) will be included as covariates in these analyses. Effect sizes between the two conditions will also be reported. Although we will test for statistical significance, as previously noted, the primary aim of this pilot study is to estimate the intervention's effect size before conducting larger, more adequately powered future studies.

VII. RISKS AND DISCOMFORTS

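### The Aim 2 efficacy test does not say how the baseline score enters the model; on its ordinary reading it is a valid change-score contrast that is less precise than a baseline-adjusted one

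*Protocol*

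**What the plan says.** Protocol section VI (Biostatistical Analysis, Specific Aim 2) says that the continuous outcomes "will be analyzed with generalized mixed effect modeling". The efficacy test is given in one sentence: "Time-by-condition interactions will be analyzed to test the efficacy of the adjunctive intervention". The covariates are given in another: "Known confounding variables (e.g., age, gender) will be included as covariates in these analyses". Effect sizes between the conditions are also to be reported, without a formula. The section adds that estimating the effect size for later trials is the main purpose.

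Hypothesis 2a in section II is worded as a greater decrease "from pre- to post-treatment than the those in the control condition", and Hypotheses 2b and 2d are likewise worded as pre-to-post change. Hypothesis 2e is worded as a level: "UP participants will report lower quantity and frequency of substance use during the study period than those in the control condition". Hypothesis 2c is also a level, at post-treatment.

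Table 1 schedules OASIS, ODSIS, BSI, CSS, the Craving Scale and the TLFB at baseline, mid-treatment and post-treatment. Section IV places the baseline assessment before randomization. Section VI plans tests of baseline balance but does not say what an imbalance would change in the Aim 2 model.

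**The concern.** Because baseline is measured before randomization, the two arms have the same baseline mean in expectation. A model that leaves the baseline means free does not use that fact. Its pre-to-post interaction subtracts the whole baseline difference, although only a fraction rho of it is expected to persist to post-treatment.

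Two things are at stake in a pilot of 50 whose main product is an effect size. The estimate is noisier than the same data allow. In the trial actually run, it also carries part of any chance baseline difference. Age and gender are not needed for the validity of a randomized comparison, whereas the baseline value of the same scale is usually the best single predictor of its later value.

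**Working it through.** **What can be reproduced.** Nothing. The sample size rests on comparison with other pilots, and no alpha, power, effect size, SD or correlation is given.

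**Inputs.**
- Sample size: "We plan to enroll 50 young adults (ages 18 to 26" (section III).
- Allocation: "Participants will be randomized in a 2:1 ratio to UP + TAU or TAU alone conditions" (section II), taken as 33:17.
- Unit of allocation: blocks of five, "2 blocks randomized to UP + TAU for every 1 block randomized to TAU alone" (section IV). Ten blocks cannot split exactly 2:1; seven against three gives 35:15.
- Assumed, not in the documents: rho of 0.3, 0.5 and 0.7 (0.8 as a further case), equal baseline and post-treatment SDs set to 1, complete data, independent participants.

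**Formulas.** Let k = 1/n1 + 1/n2. At 33:17, sqrt(k) = sqrt(1/33 + 1/17) = 0.299.
- Difference in change scores: variance 2(1-rho)k.
- Baseline-adjusted or baseline-constrained difference at post-treatment: variance (1-rho²)k.
- Ratio, adjusted to change: (1-rho²)/[2(1-rho)] = (1+rho)/2.

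| rho | SE, change | SE, adjusted | 95% half-width (1.96 × SE), change to adjusted | Variance ratio | 50 × ratio |
|---|---|---|---|---|---|
| 0.3 | 0.353 | 0.285 | 0.69 to 0.56 | 0.65 | 32.5 |
| 0.5 | 0.299 | 0.259 | 0.59 to 0.51 | 0.75 | 37.5 |
| 0.7 | 0.231 | 0.213 | 0.45 to 0.42 | 0.85 | 42.5 |
| 0.8 | 0.189 | 0.179 | 0.37 to 0.35 | 0.90 | 45 |

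The last column is the number of participants, analyzed with adjustment, that would carry the same information as 50 analyzed by change. Simulations at 33:17, which include the cost of estimating the baseline slope, gave variance ratios of about 0.67, 0.76 to 0.78 and 0.86 to 0.88 at rho 0.3, 0.5 and 0.7. At 35:15 the half-widths are 0.72 to 0.58, 0.60 to 0.52 and 0.47 to 0.43.

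**Chance imbalance.** If the arms differ by D at baseline, the expected change contrast moves by rho·D - D = -(1-rho)D. At 33:17, D has an SD of 0.299, and the probability that it exceeds 0.3 SD in either direction is 0.315. A difference of 0.3 SD moves the change contrast by 0.21, 0.15 or 0.09 SD at rho 0.3, 0.5 or 0.7. The simulated slopes were -0.70, -0.50 and -0.31, against about 0 for the adjusted estimate. With blocks of five at 35:15, the SD of D is 0.31 with no within-block correlation, and sqrt(k(1 + 4 × ICC)) = 0.34 or 0.37 at an assumed ICC of 0.05 or 0.10.

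**Sensitivity of the gain.**
- *Dropout.* In a three-wave model with equal correlations and half the losses before mid-treatment, the change-to-adjusted ratios with 20% dropout are 1.43, 1.27 and 1.14 at rho 0.3, 0.5 and 0.7. Inverted, these are 0.70, 0.79 and 0.87. With 40% dropout they are 1.33, 1.21 and 1.11, or 0.75, 0.83 and 0.90.
- *Narrower baseline spread.* With an assumed baseline SD of 0.8 of the post-treatment SD, the change variance is 1 + 0.64 - 1.6·rho, that is 1.16, 0.84 and 0.52. The adjusted variance is 0.91, 0.75 and 0.51. The ratios are 0.78, 0.89 and 0.98.

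**Does the open covariate list help?** With complete data, no. A covariate that is constant over time and enters as a main effect takes the same value before and after treatment, so it cancels from a within-person contrast. This applies to age, to gender and to the baseline score itself if it is added in that way to a three-wave model.

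**What if only mid and post are outcomes?** With baseline as covariate, the time-by-condition interaction tests only whether the arms diverge between mid and post. The efficacy contrast would then have to be the arm difference at post-treatment.

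**The case against.** The strongest objection is that the weakness is inferred. The protocol does not say that the baseline means are free, its covariate list is open, and a baseline-constrained model also expresses its effect as a time-by-condition interaction. A statistical analysis plan, not available here, could settle the mean structure. This stands in part: the wording does not exclude the better model. But the protocol does name the test, and with three waves and hypotheses about pre-to-post change its ordinary reading is a difference in change. Adding covariates as main effects does not alter that.

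A reader might infer more, and the documents do not support it:
- *That the plan ignores baseline.* It does not. Baseline is a repeated outcome and is subtracted.
- *That the analysis is biased or invalid.* Under no effect, both estimators averaged about 0 in simulation. The shift is conditional on the imbalance that happens to occur.
- *That a fixed loss applies to every outcome.* It depends on an unknown rho, on equal SDs and on complete data. Hypothesis 2b restricts BSI to those with past-month suicidal thoughts at baseline, so the 33:17 figures do not apply to it. PDA is bounded and falls under Hypothesis 2e, which is worded as a level, so the linear formula does not describe it well.
- *That the reported effect size will be a change-score effect.* No formula is given for it.

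Entry on elevated distress could also narrow the baseline spread, which reduces the gain as shown above.

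**Conclusion.** The point holds as an available improvement, not as an error that invalidates the plan. On the ordinary reading, and under the stated assumptions, the change-score contrast has 54%, 33% or 18% more variance than the baseline-adjusted one at rho 0.3, 0.5 or 0.7 (1/0.65, 1/0.75, 1/0.85), and 11% more at rho 0.8. It also carries (1-rho) of any chance baseline difference in the trial at hand. These figures are for full-sample continuous scales. They shrink with dropout and with a narrower baseline spread, and rho is an assumption throughout. The change is worth making because no power calculation supports the sample size, the effect size is the main product, and the baseline values are already collected. If the analysis plan already constrains or adjusts for baseline, the protocol sentence needs only to be brought into line with it.

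**What to change.** For OASIS, ODSIS, CSS, the Craving Scale, and BSI within its subgroup, define both the treatment effect and the reported effect size as the arm difference at post-treatment, from a mixed model in one of two forms:

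1. baseline, mid and post as outcomes, with baseline means constrained equal across arms; or
2. mid and post as outcomes, with the baseline value as covariate. Here the test is the arm difference at post-treatment, not the mid-to-post interaction.

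For PDA and substance use, adjust the study-period level for the baseline TLFB value in a model suited to a bounded or count outcome, which also fits the wording of Hypothesis 2e.

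Replace the sentence "Known confounding variables (e.g., age, gender) will be included as covariates in these analyses" with one that names the baseline value of the outcome, plus age and gender.

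The cost is a few lines in section VI. No new data, visits or change to the randomization are needed.

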UP + TAU condition: After randomization, participants randomized to the UP + TAU condition will undergo TAU at ARMS and be offered 16 additional, twice-weekly group UP sessions, also at ARMS (see *Intervention*). Participants in the UP + TAU condition will undergo the same midand post-treatment assessments as the TAU condition, plus the CSQ-8 and a semi-structured interview to collect feedback about the intervention (see *Measures*). The mid-treatment assessment will occur after each participant's 8th UP session OR between 4-6 weeks after randomization, and the post-treatment assessment will occur within two weeks after each participant's 16th UP session. The same risk assessment procedures for mid- and post-treatment assessments used in the TAU condition will also apply to the UP + TAU condition. Should a UP + TAU participant condition have two consecutive unplanned absences from a UP group session, up to three attempts to contact will be made regarding their absence. There will not be a maximum number of missed UP sessions warranting a participant to step out of the 16-session group protocol. After completing the post-treatment assessment, their participation in the study will be complete.

Group UP sessions will take place at the ARMS program at MGH. Study assessment visits (screening/baseline, mid-treatment, and post-treatment) may take place at the ARMS program, the Depression Clinical and Research Program (DCRP), or the Center for Addiction Medicine (CAM) at MGH. Study staff may walk participants between ARMS and the DCRP or CAM as needed.

In sum, the proposed study involves the following points of contact: (1) obtaining informed consent and screening/baseline assessment, (2) mid-treatment assessment involving self-report questionnaires and TLFB, (3) post-treatment assessment involving self-report questionnaires and TLFB (primary endpoint), and (4) 16 twice-weekly group UP sessions for those randomized to the UP + TAU condition.

If participants are unable to complete the clinician-rated measures in-person at their mid- or post-treatment assessments, they will be given the option to complete this portion of the visit via phone call with a study clinician. Should any risk issues arise, the clinician will complete a risk assessment while on the phone with the participant. A licensed clinician will always be on-site for consultation as needed during assessments conducted over the phone.

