If participants are unable to complete the self-reported measures in-person at their screening/baseline, mid-treatment, or post-treatment assessments, they will be e-mailed a link to the self-report battery in Redcap to complete remotely. Study staff will review the completed SRQ assessment in Redcap within 24 (business) hours of submission for report of suicidal thoughts, and within one week to assure their completeness. Should a participant report suicidal thoughts in the past week on the SITBI-SR, a clinical risk assessment (including severity of ideation and presence of plan, intent, and access to means) will be conducted over the phone by a study clinician to ensure participant safety and that the participant remains stable to be treated in an outpatient setting. Additionally, a clinical risk assessment will be conducted over the phone by a study clinician in response to reports of increased NSSI that are deemed clinically

significant. Up to three attempts to contact will be made for this risk assessment before calling a participant's designated emergency contact.

Participants may receive recruitment and scheduling messages, as well as appointment reminders via e-mail or text message over the course of the study, depending on their preferred method of communication. Up to three consecutive (unanswered) contact attempts to the participant will be made for participants in both conditions to schedule mid- and post-treatment assessments. If a participant misses the mid-treatment assessment, but is still responsive to contact attempts, they will still be able to complete the post-treatment assessment. If a participant in either condition is unresponsive to three consecutive unanswered contact attempts within a three-week period at any point within the 10-week study, they will be considered dropped out from the study and no further follow-up will be made; the ARMS clinical team will also be notified.

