There are some potential risks and burdens to participating in the study. Risks and discomforts associated with receiving psychotherapy are generally considered modest, but can include a worsening of psychiatric symptoms as well as psychological discomfort associated with discussion of one's difficulties and potentially emotionally-provoking experiential exercises. For group psychotherapy specifically, participants may also feel uncomfortable sharing personal information in front of others and experience a triggering of distressing thoughts and feelings while listening to others discuss sensitive issues related to substances use and emotional health. Participants will be given telephone numbers of the clinicians involved in the study if they would like to talk about any discomforts and will be able to stop the study intervention at any time without penalty. All group leaders are also skilled in delivering group therapy and navigating group discussion of sensitive topics. Second, answering detailed questionnaires and undergoing clinician interviews regarding substance use and psychological problems may create a mild degree of discomfort. For the possibility of subjective discomfort from answering questions, distress will be minimized by assurance that participants can refuse to answer any question that they do not feel comfortable addressing and may withdraw from the study at any time without penalty. Further, study clinicians are skilled in talking about sensitive information with subjects, and subjects may decide to end an interview at any time. Third, coming in for UP group sessions and/or assessments may be seen as time-consuming and inconvenient. For study visits involving assessments and not treatment, we have provided compensation for subjects' time, commensurate with hourly compensation for non-treatment studies being conducted at MGH. We have also provided compensation for up to two weekly treatment sessions, commensurate with the approximate costs of travel.

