Safety Monitoring: Participants' suicidality and homicidality will be assessed by a study clinician for degree of immediate risk (plan of harm, intent to harm, means to harm) at each assessment visit. If a participant is determined to be at imminent risk of harm, a transfer to the MGH emergency room will be facilitated immediately for further evaluation. If additional treatment is warranted (e.g., inpatient hospitalization), the PI will assess the appropriateness of the participant's continuation in the study based on the exclusion criteria and clinical well-being of the individual. The PI will continue to monitor the mental status of participants and/or discontinue participation in the study if appropriate. Participants will be dropped from the study for unstable mental health rendering them inappropriate to be treated in an outpatient setting (e.g., new onset SI/HI with intent and/or plan) and/or severe noncompliance with study procedures.

Continued drug use and alcohol consumption is to be expected to some degree with outpatient treatment, including at ARMS specifically. This will be monitored throughout the treatment period. If a participant presents with acute alcohol or drug intoxication to a study assessment visit or UP group session and is determined (by a study clinician) to require emergency services, a transfer to the MGH emergency room will be facilitated immediately. Participants' involvement in the study will not be disclosed to emergency services.

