Adverse Event Reporting: Consistent with good clinical practice, safety will be closely monitored by study staff. The PI will oversee all study activities including self-report and clinician ratings. All procedures have been designed to minimize subject discomfort, and no subject will be asked to engage in research procedures not outlined in the consent form. Subjects will be monitored for adverse events at each assessment visit by a study clinician. All adverse events (including unexpected and serious AEs) will be recorded and reported in accordance with Partners HealthCare guidelines. A subject may be dropped from the study at any time due to adverse events. We will follow and adhere to all guidelines as defined and outlined on the Partners Human Research Committee web site:

http://healthcare.partners.org/phsirb/adverse.htm. The PI will be responsible for ensuring that adverse events are reported to the local IRB in compliance with local and federal requirements. Any changes to the protocol will be made in accordance with MGH IRB policies.

Data Monitoring: The PI will be responsible for ongoing quality control, including data integrity and protocol compliance. All clinician-rated data will be collected on paper and entered into Redcap. All self-report data that is collected on paper will be entered into Redcap. If a participant is unable to complete self-report measures in person, the data will be entered directly into Redcap remotely by the participant. To ensure usability of self-report data, a member of study staff (whoever is conducting the assessment) will review all self-report measures within one week of submission to insure their completeness. All self-report assessment forms and clinician-administered instruments will be reviewed by study staff within one week of their completion to assure that they are being completed correctly. Any errors in completion will be reviewed to determine if directions or procedures for the assessments need to be altered. In this case, permission from the IRB will be requested to change any procedure. The group sessions will also be audiotaped (with subjects' permission) and a random selection will be rated for competence and adherence to the protocol. This will also ensure the usability of the data.

Confidentiality:

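### Safety removals end study participation, not only UP sessions, so post-treatment Aim 2 scores can be lost because of the outcome

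*Protocol*

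**What the plan says.** **Removal rules (Section IX).** Safety Monitoring states removal as a firm rule: "dropped from the study for unstable mental health rendering them inappropriate to be treated in an outpatient setting (e.g., new onset SI/HI with intent". The example goes on to name a plan as well. If further treatment such as hospitalization is needed, the PI judges the participant's "continuation in the study based on the exclusion criteria and clinical well-being of the individual". Adverse Event Reporting adds: "A subject may be dropped from the study at any time due to adverse events". All three passages concern the study as a whole and apply to both arms.

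**Assessments (Section V).** The post-treatment visit is the key time point: "post-treatment assessment involving self-report questionnaires and TLFB (primary endpoint"). A report of past-week suicidal thoughts on the SITBI-SR leads to a clinical risk assessment "to ensure participant safety and that the participant remains stable to be treated in an outpatient setting". Someone who misses the mid-treatment visit but "is still responsive to contact attempts, they will still be able to complete the post-treatment assessment". If clinician-rated measures cannot be done in person at mid- or post-treatment, "they will be given the option to complete this portion of the visit via phone call with a study clinician", and self-report measures can be completed through an e-mailed REDCap link.

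**Stopping treatment (Section VII).** Participants "will be able to stop the study intervention at any time without penalty"; withdrawal from the study is mentioned separately.

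**Analysis (Section VI, Specific Aim 2).** The analysis is by allocated group regardless of treatment received, using a mixed model that handles missing values by maximum likelihood.

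**The concern.** The removal criterion and the Aim 2 outcomes measure much the same thing. Aim 2 concerns anxiety, depression, suicidal ideation and NSSI, and the trigger for removal is a severe form of these. The check that follows a SITBI-SR report asks whether the person is still fit for outpatient care, which is also the test for removal. A participant removed before the post-treatment visit therefore has no primary-endpoint score because of how badly he or she was doing.

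Stopping outpatient group treatment in a crisis is right. Ending outcome collection is a separate step that safety does not require. Section VII names worsening of psychiatric symptoms as a possible risk of the treatment, and the scores at risk belong to the people who worsened most. If UP caused more such crises, the Aim 2 effect sizes would be pulled toward no harm. Estimating an effect size for later trials is a stated purpose in Section VI, alongside feasibility and acceptability. Hypothesis 2b uses only participants with past-month suicidal thoughts at baseline, so each lost score weighs more there.

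**Working it through.** **1. Does removal mean loss of assessments?**

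- The rules cover both arms. Apart from attendance payments, a TAU participant receives nothing from the study except assessments, so removal from the study can hardly mean anything but an end to assessments.
- The one place that says what follows dropout (Section V, non-responders) ends follow-up.
- Where the protocol wants an assessment kept, it says so, as for the missed mid-treatment visit. Missed UP sessions also do not lead to removal. No such provision follows a safety removal.

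**2. When is a score lost?** It depends on timing.

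- Crisis found at the post-treatment visit: it can be scored, and nothing is lost.
- Crisis found at mid-treatment: scored there; only the post-treatment score is lost.
- Crisis and removal between visits: not scored at all.

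**3. How large could the distortion be?** The protocol gives no crisis rate, SD or dropout rate, so there is no figure of its own to reproduce. Only N = 50 and the 2:1 ratio (about 33/17) come from the document. The rest is assumed:

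- three visits, unit variance, correlation ρ = 0.6;
- a crisis adds δ = 2 SD, and its log-odds rise by 1 per SD of the preceding score;
- crisis risk q is 15% or 10% in UP + TAU and 5% in TAU;
- the share d of crises removed is the same in both arms.

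A large-sample simulation (400,000 per arm, maximum likelihood with unstructured covariance) gives these UP-minus-TAU differences at post-treatment, in SD, where positive means harm:

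| Crisis rates and timing | True | d = 50% | d = 80% | d = 100% |
|---|---|---|---|---|
| 15% v 5%, between mid and post | 0.20 | 0.11 | 0.05 | 0.00 |
| 15% v 5%, scored at mid, persisting | 0.20 | 0.16 | 0.12 | 0.07 |
| 15% v 5%, scored at mid, half resolved | 0.10 | 0.09 | 0.08 | 0.075 |
| 10% v 5%, between mid and post | 0.10 | 0.06 | 0.02 | 0.00 |
| 10% v 5%, scored at mid, persisting | 0.10 | 0.08 | 0.06 | 0.04 |

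For 15% v 5%, a random-intercept model gives 0.111, 0.048 and −0.001 in the first row and 0.147, 0.111 and 0.076 in the second.

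*Hand check, between visits.* The true difference is 0.15 × 2 − 0.05 × 2 = 0.20. Among those still observed, an arm's mean shift is q(1 − d)δ / (1 − qd).
- d = 0.5: 0.15/0.925 − 0.05/0.975 = 0.162 − 0.051 = 0.111.
- d = 0.8: 0.06/0.88 − 0.02/0.96 = 0.068 − 0.021 = 0.047.
- d = 1: 0.

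*Hand check, scored at mid, d = 1.* The model predicts the missing post score from baseline and mid. The coefficient on mid is ρ/(1 + ρ) = 0.6/1.6 = 0.375, so it carries forward 0.375 × 2 = 0.75 SD per crisis, and (0.15 − 0.05) × 0.75 = 0.075. That is well short of 0.20 if the crisis persists and close to the true 0.10 if it half resolves.

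*No difference.* With equal crisis rates and equal removal, the bias is zero within simulation error (0.003).

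*Numbers removed.* At 15% v 5%: 33 × 0.15 × d + 17 × 0.05 × d = 2.9, 4.6 and 5.8 for the three values of d. At 10% v 5%: 2.1, 3.3 and 4.2. So about 2 to 6 of 50.

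*Sampling error.* √(1/33 + 1/17) = 0.299 SD.

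**4. A second set of assumptions.** Take a true benefit of −0.50 SD, with the post score missing for the worst-scoring fraction of each arm. The likelihood estimate becomes −0.40 (3% UP v 12% TAU removed), −0.36 (6% v 18%) or −0.57 (12% v 6%). It stays at about −0.50 when removal is equal (6% or 12% in both arms), and in every scenario where the observed mid score fully explains removal.

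**The case against.** The strongest reply is that the loss is inferred from silence. The protocol says explicitly that follow-up ends for non-responders and does not repeat this for safety removals; the adverse-event rule is permissive; and the PI decides case by case after hospitalization. The scheduled risk checks also sit at visits where scores are collected, so the worst case (an unscored crisis between visits) may be uncommon. Every number above is assumed, the distortion is smaller than the sampling error, and Aim 2 is exploratory in a 50-person pilot.

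Much of this stands as a limit. Not every crisis ends participation, so the 100% column is an extreme. A difference in removal between arms is possible but not shown, and neither the size nor the direction of bias can be derived from the protocol. There is also no literal contradiction with the intention-to-treat statement, because removed participants stay in their arm with the scores they have. Safety oversight is not impaired: the DSMB and IRB still receive serious adverse events.

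It does not remove the point. The mental-health rule is mandatory as written, and for TAU participants it has little meaning other than ending assessments. The comparison of dropouts with completers in Section VI describes the loss but cannot recover uncollected scores, and neither can a later analysis plan. It is true that substance-use data from someone moved to inpatient care would partly reflect restricted access. That affects the TLFB outcomes, not the BSI, OASIS, ODSIS or SITBI. Whether an acutely ill person can be approached is a clinical judgement, which the proposed wording leaves in place.

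**Conclusion.** The concern holds. Followed as written, Section IX ends study participation for people in a severe state of the Aim 2 outcomes, with nothing to preserve their later scores. That undercuts the complete follow-up on which an analysis by allocated group relies, and maximum likelihood repairs it only in part. Under the assumed 15% v 5% crisis rates and 2 SD shift, a true harm of 0.20 SD shrinks to between 0.00 and 0.16 SD, depending on timing and the share removed. With half-resolved crises scored at mid-treatment the loss is at most 0.025 SD, and with no true difference and equal removal it is nil. The effect is confined to the Aim 2 effect sizes and is smaller than the 0.30 SD standard error, but it is systematic and cheap to prevent, so the protocol should be changed.

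**What to change.** Amend the Safety Monitoring sentence in Section IX. Participants whose mental health makes outpatient treatment inappropriate stop UP sessions and are referred for care, but remain in the study. Their mid- and post-treatment assessments are offered on the original schedule when they are clinically able, in person, by phone or by REDCap link, unless they withdraw consent. Make the same change to the Adverse Event Reporting sentence. Report by arm the number stopped or removed for safety, with time and reason.

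The cost is two amended sentences and IRB approval. The phone and REDCap routes, the review of remote responses for suicidal thoughts within 24 business hours, and the $50 post-treatment payment already exist. Staff would need to contact a few acutely ill participants, about 2 to 6 of 50 under the assumed rates. Some will be unable or unwilling, so some scores will still be missing.
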